During the first four study treatment administrations, patients will be monitored for acute hypersensitivity reactions for at least 60 minutes after the end of the injection. Epinephrine and parenteral diphenhydramine must be readily available for immediate use if required to treat a hypersensitivity reaction; site personnel must be able to detect and treat such reactions. Patients with severe hypersensitivity reactions (e.g., stridor, angioedema, life-threatening change in vital signs) must be withdrawn from study treatment. These patients are to enter the 12-week safety follow-up in this study followed by PML monitoring in Part 2 (SM) of this study.

All adverse events of systemic hypersensitivity reactions or anaphylactoid or anaphylaxis reactions must be reported within 24 hours to the Sponsor and the Medical Monitor must be informed as soon as is practical (see the Study Manual for contact information).

Following the first four drug administrations (typically expected at 12 weeks), study drug administration will be continued in the home setting by the patient or a caregiver if considered appropriate by the investigator. If a caregiver is administering the injection, the outer area of the upper arm may be used in addition to the abdomen or thigh. If a patient is administering the injection to themselves, they are not allowed to administer the injection in their upper arm. Study medication will be administered in the patient’s home after return from the clinic visit on days when drug administration is to take place

on the same day as a clinic visit day. Patients and/or the caregiver will be provided with contact information for questions related to self-administration between visits. Competence of the patient or caregiver to administer at home will be documented in source documents. Compliance in the home setting is to be monitored by use of a patient diary to record drug administration and return of used and unused medication syringes. Patients and/or the caregiver will be provided with alert cards for themselves and a partner/caregiver, which they will be requested to carry at all times. These will include guidance on recognizing allergic/anaphylactic/anaphylactoid reactions and how to obtain emergency care in the event such a reaction occurs and information regarding recognition of symptoms of PML.

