5.4.6.1 Injection-Site Reactions

Local cutaneous adverse events that occur at or around the injection site during or within 24 hours after study drug injection should be captured as individual signs (e.g., erythema, induration/swelling at injection site) and symptoms (e.g., pain, pruritus at injection site) rather than a diagnosis of allergic reaction or injection site reaction.

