6.3.1 Adverse Events

Verbatim descriptions of treatment-emergent adverse events will be coded and their incidence and observation time-adjusted rate will be summarized, as appropriate. A treatment-emergent adverse event is defined as any new adverse event reported or any worsening of an existing condition on or after the first dose of study drug. In addition, separate summaries will be generated for serious adverse events, deaths, and adverse events leading to discontinuation of etrolizumab.

Analyses will also be performed for:

- Systemic hypersensitivity events

Specific analyses will be performed for anaphylactic reactions using both the anaphylactic reaction MedDRA SMQ and Sampson's criteria (see [Appendix 10 Clinical Criteria for Diagnosing Anaphylaxis](#)).

- Serious infections, in particular GI infections
- Opportunistic infections
- Malignancies
- Injection-site reactions

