4.1 GENERAL CONSIDERATIONS

4.1.1 Analysis of Study Conduct

The number of patients who discontinued early (early discontinuation of OLE treatment or early termination from the study) or completed the study will be tabulated.

Reasons for early discontinuation of treatment or early termination from the study will be listed and summarized. Any eligibility criteria exceptions and other major protocol deviations will also be summarized.

Since Part 1 (OLE) of GA29145 was terminated by the Sponsor on 15th February 2022, no patients are expected to reach treatment completion. As a result of this, the end of Part 1 (OLE) of GA29145 is defined from the last dose date in GA29145 on 15th May 2022.

In summary, the following will be summarised for GA29145 Part 1 (OLE):

- Analysis populations
- Patient disposition
- Study treatment completion/discontinuation
- Study completion/discontinuation
- Major protocol deviations
- Exposure

Treatment Labels

For the OLE population, the only treatment arm to be summarized is:

Group	Patients Included
OLE Etrolizumab	Patients in the OLE population who receive at least one dose of etrolizumab in Study GA29145 Part 1 (OLE)

All tables should be presented by treatment group only.

Part 1 (OLE) Day 1

OLE Study Day 1 is defined as the day patient has the first receipt of study drug in GA29145 Part 1 (OLE).

Baseline

Baseline is defined as the last available assessment prior to first receipt of study drug in the Induction Phase of the parent study, GA29144.

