Summary tables will be generated for AEs, serious adverse events (SAEs), deaths, AEs leading to discontinuation of study drug, and AESIs. A listing will be generated for AEs, deaths, selected AESIs/specific AEs, and COVID-19 AEs. Pregnancies will be reported as narratives in the study CSR.

Summary tables of AEs will summarize the incidence of treatment-emergent AEs only. Treatment-emergent events are defined as any new AE reported on or after the first dose of OLE study drug or any worsening of an existing condition. Note that worsening of existing conditions include AEs ongoing from the parent study, GA29144. Otherwise, only AEs reported on or after the first dose of OLE study drug are included. If the onset date of the AE is prior to the day of first dose, the AE will be considered treatment emergent only if the most extreme intensity is greater than the initial intensity (i.e., the intensity for a given AE increases and its end date is on or after the date of the first dose). For all summary tables, the AEs will be sorted by SOC (in decreasing order of overall incidence) and then by preferred term (PT) (in decreasing order of overall incidence).

For OLE etrolizumab treatment, the incidence count for each AE PT will be defined as the number of patients reporting at least one treatment-emergent occurrence of the event (multiple occurrences of the same AE in 1 patient will be counted only once). The proportion of patients with an AE will be calculated as the incidence count divided by the total number of patients in the population. Each table will also present the total number of AEs reported where multiple occurrences of the same AE in an individual are counted separately.

Rate tables will be generated for selected AEs of interest. The rate per 100 patient years and 95% CIs will be summarized by treatment group and will be calculated by:

$$AE \text{ Rate (per 100 patient years)} = \frac{\text{Total number of AEs (in OLE only)}}{\text{Total number of patient years at risk (in OLE only)}} \times 100$$

where the total patient-years at risk is the sum over all patients of the time intervals (in years) from the first dose of study treatment in Part 1 (OLE) until the patient completes/withdraws from the study (including the 12-week safety follow-up, if applicable). Only treatment emergent AEs with an onset date after the first dose of open label Etolizumab in GA29145 will be included within these outputs.

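### SAP 4.2.2 rate tables admit only AEs with an onset date after the first OLE dose, so a literal date rule drops Day 1 events that the treatment-emergent definition and the patient-years both include

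*SAP*

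**What the plan says.** SAP 4.2.2 (Adverse Events) sets three rules that meet at the first OLE dose.

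- **Treatment-emergent definition.** "Treatment-emergent events are defined as any new AE reported on or after the first dose of OLE study drug", together with worsening of an existing condition. A later sentence repeats the on-or-after boundary. For AEs carried in from the parent study, the test is by calendar day: "If the onset date of the AE is prior to the day of first dose", the event counts only if it worsened.
- **Rate denominator.** Each patient contributes time "from the first dose of study treatment in Part 1 (OLE) until the patient completes/withdraws from the study", including the 12-week safety follow-up where it applies.
- **Rate numerator.** "Only treatment emergent AEs with an onset date after the first dose of open label Etolizumab in GA29145 will be included within these outputs".

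SAP 4.1.1 defines OLE Day 1 as the day of the first OLE dose. SAP 4.2.2 promises rate tables for a selection of AEs but does not list them. SAP 1.3.2 names a rate for infection-related AEs and for malignancies only. Hypersensitivity and injection-site reactions are specified there by incidence and severity.

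Protocol 6.3.1 also uses an on-or-after boundary for treatment-emergent events: "any worsening of an existing condition on or after the first dose of study drug". SAP 4.4 records no change on this point.

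**The concern.** A rate should count events over the same time that its denominator covers. If the numerator rule is programmed as onset date strictly later than the date of the first OLE dose, Day 1 adds person-time but can never add an event. The incidence tables would count the same Day 1 event, because their boundary is inclusive.

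The events most exposed to this boundary are acute reactions to the first injection. Protocol 5.4.6.1 captures injection-site reactions "during or within 24 hours after study drug injection". For the first four doses, Protocol 4.2.2 states that "patients will be monitored for acute hypersensitivity reactions for at least 60 minutes after the end of the injection". A reaction to the first OLE dose would therefore usually carry a Day 1 onset date. If such reactions were given a rate table, the rule would remove part of what the table is meant to show.

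**Working it through.** The plan states no AE rate, event count or mean follow-up, so there is no figure to reproduce. The check compares the rules and then sizes the gap.

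**1. The rules for an AE with onset on OLE Day 1, read by calendar date**

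- Incidence tables (on or after): counted.
- Patient-years (from the first dose): Day 1 included.
- Rate numerator (onset date after): not counted.

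For an AE with onset before Day 1 that worsened in the OLE:

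- Incidence tables: counted.
- Rate numerator: not counted, whether the rule says after or on or after.

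Only the Day 1 difference comes from the choice of word.

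**2. Events spread evenly over follow-up (infections, malignancies)**

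Share of events lost = 1 day / days of follow-up.

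- A patient followed to Week 108 plus the 12-week follow-up: (108 + 12) × 7 = 840 days, and 1/840 = 0.12%.
- At an assumed mean follow-up of T years, share = 1/(365.25 × T): 0.27% for T = 1, 0.14% for T = 2, 0.07% for T = 4.

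In events, using the SAP's maximum of about 1150 patients, Day 1 amounts to 1150/365.25 = 3.15 patient-years.

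- At an assumed 30 events per 100 patient-years, the loss is 0.30 × 3.15 = 0.9 events. The reported rate would be 29.92, 29.96 or 29.98 for T = 1, 2 or 4, against 30.00.
- At an assumed 0.5 per 100 patient-years, the loss is 0.005 × 3.15 = 0.02 events.

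**3. Acute reactions, only if they are given a rate table**

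Let s be the share of events with Day 1 onset. The patient-years do not change, so

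reported rate = rate on an on-or-after basis × (1 − s).

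The documents do not give s. Two assumed values show the arithmetic:

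- Equal risk at each dose scheduled from Week 0 to Week 108: 108/4 + 1 = 28 doses, so s = 1/28 = 3.6%.
- s = 10%, with an assumed 115 events in 1150 × 2 = 2300 patient-years. On or after gives 115/2300 × 100 = 5.00 per 100 patient-years (exact Poisson 95% CI 4.13 to 6.00). Strictly after leaves 115 × 0.9, about 104 events, and 104/2300 × 100 = 4.52 (3.69 to 5.48).

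These are illustrations of a table that the SAP does not name, not estimates for this trial.

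**The case against.** The strongest reply is that the sentence is ambiguous rather than wrong. It begins from the treatment-emergent set and narrows it, and its evident job is to keep worsened parent-study AEs out of the rates. Where the section means a calendar day, it says day or date of the first dose. Here it says the first dose. If the dose is read as a moment in both rules, a reaction after the injection is counted and the numerator matches the denominator.

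That reading is possible. However, the rule is tied to the onset date, the section names no onset time, and two programmers could reasonably code it differently. The same section states that the dates are inclusive for its COVID-19 window, so it can fix a boundary where it chooses to. The reply supports a mild grading but does not remove the need to clarify. The presumed purpose also survives the fix, because an on-or-after rule still excludes earlier onsets.

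Two further replies stand in full. First, Protocol 6.3.1 is not good evidence against the SAP. The SAP states that its analyses supersede the protocol's, and the protocol's definition includes worsening, which the corrected rate rule would also leave out. The case rests on the mismatch inside SAP 4.2.2. Second, nothing shows that a named outcome is materially affected.

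A reader might infer that the trial's reaction risk will be understated, perhaps by a large fraction because the first four doses are observed in clinic. The documents do not support this. Reactions are planned as incidence and severity, and those tables use the inclusive boundary. No rate table for reactions is named. Protocol 4.2.2 and 5.1.1.4 also provide for reporting injection-site reactions at home, so reactions cannot be assumed to stop after the fourth dose. Nor do the documents show that the single pooled OLE column is an error: it follows the safety set in Protocol 6.3, and no objective asks for results by prior etrolizumab exposure.

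**Conclusion.** The mismatch is real and sits in the current SAP text, but it is minor. Read by calendar date, the rate numerator excludes Day 1 onsets that the treatment-emergent definition and the patient-years include.

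For infections and malignancies the relative effect is under 0.3%, assuming events spread evenly and a mean follow-up of at least one year. For injection-site or hypersensitivity reactions the rate would be too low by exactly the Day 1 share of events, but only if they are among the unlisted events chosen for rate tables. That condition is open, not established, and the share is unknown. Incidence tables do not change under either reading.

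A reader might also infer that incidence and rate tables ought to agree event for event. They will not, even after correction: worsened AEs from GA29144 belong to the incidence tables only, and that difference is intended.

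**What to change.** In SAP 4.2.2, reword the rate-table rule to: *treatment-emergent AEs with an onset date on or after the date of the first OLE dose; AEs with an earlier onset, including worsened AEs carried over from GA29144, are excluded.*

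The cost is one phrase in the SAP and one comparison operator in the program. No data collection, population or denominator changes. A date-only rule can admit a Day 1 AE that began before the injection, but the incidence tables already accept this. A table footnote could say that rate tables omit worsened parent-study AEs, so that the remaining difference from the incidence tables is not taken for a mistake.

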4.2.3 Additional Safety Assessments

4.2.3.1 Laboratory Data

Selected laboratory parameters for safety reporting will be described further in the OLE population by summarizing the marked abnormalities and shift tables. Marked abnormalities will be identified according to a Sponsor-defined standard, which generally captures post-baseline laboratory values both outside a reference range and achieving a threshold percent change from baseline. Where needed, laboratory values will be linearly transformed to a standard reference range in order to account for intrinsic differences between males and females or measurement differences between laboratory standards.

Laboratory abnormalities and the patient's worst Common Terminology Criteria for Adverse Events (CTCAE) grade during study will be summarized for hematology and serum chemistry parameters, in addition to change from Baseline summaries.

Elevated liver enzyme tests will be summarized by the following upper limit of normal (ULN) categories as these are indicators of severe liver injury:

- ALT or AST > 3ULN and total bilirubin > 2 ULN as defined by Hy's law
- ALT or AST > 3 ULN

4.2.3.2 Vital Signs

Vital signs will be summarized using summary statistics and change from baseline. The proportion of patients experiencing clinically significant changes relative to baseline will be reported if appropriate.

4.2.3.3 ECGs

A shift table for the qualitative ECG assessments will be produced, summarizing the Baseline and worst post-baseline results.

4.2.3.4 Medical History

Medical history data collected in the electronic-CRF (eCRF) from OLE Day 1 will be summarized using summary statistics, reporting the proportion of patients with at least one medical condition and the total number of medical conditions. The medical conditions will then be split out by type.

4.2.3.5 Concomitant Medications

Concomitant medications include any medication being used at any time from first dose of OLE study drug through to 7 days after last dose of OLE study drug. The data will be summarized, and report the total number of patients taking at least one medication, and total number of medications. Summaries will also be split by medication class and preferred medication. Medication terms will be mapped and reported using the WHO drug dictionary.

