4.3 CONCOMITANT THERAPY

4.3.1 Permitted Therapy

Part 1 (OLE)

Concomitant therapy includes any medication (e.g., prescription drugs, over-the-counter drugs, herbal/homeopathic remedies, nutritional supplements) used by a patient from the start of the study to completion/early withdrawal from treatment.

Patients who use oral contraceptives or maintenance therapy for comorbidities should continue their use.

At any time during the study, patients who have worsening CD may receive concomitant therapy with corticosteroids (IV, oral, or topical) at the discretion of the investigator.

All concomitant medications should be reported to the investigator and recorded on the Concomitant Medications eCRF. All concomitant medications ongoing in Study GA29144 must be recorded on the Concomitant Medications eCRF for this study.

Patients taking immunosuppressants in Study GA29144 may continue to receive immunosuppressants in the OLE-SM study or may initiate immunosuppressant treatment with dose adjustments at the discretion of the investigator. Generally accepted criteria for discontinuation of immunosuppressant due to toxicity include, but are not limited to, acute pancreatitis, severe leukopenia, severe thrombocytopenia, or clinically significant elevations of the liver-associated enzymes from baseline, especially in the presence of an elevated total bilirubin. The ultimate decision to discontinue or reduce dose of immunosuppressant remains at the discretion of the investigator.

Part 2 (SM)

During Part 2 (SM), investigators should follow standard practice and prescribe the local standard of care or treatments that in their opinion meet the needs of the patient.

ONLY concomitant medications used to treat event-related neurological abnormalities that are recorded and ongoing on the Adverse Event eCRF during Part 2 (SM) must be entered on the Concomitant Medication eCRF.

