4.4.4.9 Concomitant Medications

Concomitant medications will be monitored and reviewed at each study visit, including any unscheduled visit(s).

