5.1.1.7 Decreased Effectiveness of Immunizations Background

The effect of etrolizumab upon the efficacy of vaccinations is unknown.

Patient Selection and Risk Mitigation

Patients who received a live attenuated vaccine during Study GA29144 or within 4 weeks prior to enrollment in the OLE are excluded from the study. Patients should not receive live attenuated vaccines during the study and for at least 5 half-lives (approximately 12 weeks) after final study drug administration.

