Note: All assessments and blood draws are to be conducted prior to study medication administration.

^a Day 1 of Week 0.

^b Week 0 procedures and laboratory assessments that have been performed as part of the final visit for Study GA29144 do not need to be repeated, with the exception of ATAs, which must be recollected at Week 0 if the Week 0 visit occurs >7 days after the final visit for Study GA29144.

Appendix 1

Open-Label Extension (OLE, Part 1) Schedule of Assessments (cont.)

- ^c Assessments in this column should be conducted in addition to the assessments conducted every 12 weeks.
- ^d Assessments in this column should be conducted in addition to the assessments conducted every 12 weeks and every 48 weeks.
- ^e Unscheduled visit represents a visit that is not as per Schedule of Assessments and is required for an adverse event or for potential relapse assessment. All indicated assessments are NOT performed at each unscheduled visit. Assessments would be symptom driven (e.g., only perform PML neurologic examination if patient reports symptoms suspected to indicate PML). Assessments corresponding to items noted in this column should be recorded on the eCRF.
- ^f Denotes the early withdrawal from treatment visit for the open-label treatment period. To be performed within 30 days of last dose of study drug. Study drug is not administered at the Early Withdrawal from Treatment visit.
- ^g Patients will be given patient alert cards that provide information regarding the signs and symptoms of PML. Patients will be instructed to contact the study site at any time if they develop any new neurological signs or symptoms suggestive of PML.
- ^h Patient diary check (including completion of abdominal pain questionnaire), CDAI assessment, and recording patient's weight are required at study completion. Conduct CDAI assessment and record patient's weight at early withdrawal visit if diary-data captured prior to the early withdrawal visit are available.

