Appendix 2 12-Week Safety Follow-Up (OLE, Part 1) Schedule of Assessments

Part 1 (OLE)	Week (± 7 days)		Unscheduled Visit ^c
	6 ^a	12/Early Withdrawal Visit ^b	
Concomitant medications	x	x	x
Adverse events	x	x	x
Urine pregnancy test ^d		x	
Anti-therapeutic antibody sample (serum) ^e		x	
PML assessment interview ^f		x	x ^g
Neurological examination ^{f, h}		x	x ^g

ATA = anti-therapeutic antibody; JCV = John Cunningham virus; OLE = open-label extension; PML = progressive multifocal leukoencephalopathy.

- ^a Week 6 study assessments are to be made by telephone visit and not by clinic visit.
- ^b If the patient discontinues prior to completion of the 12-week safety follow-up, the indicated assessments for the 12-week safety follow-up clinic visit should be performed as the Early Withdrawal visit of the safety follow-up period.
- ^c Unscheduled visit for safety monitoring.
- ^d For women of childbearing potential, including those who have had a tubal ligation, perform a urine pregnancy test; if the urine pregnancy test result is positive, confirm with a serum pregnancy test.
- ^e If serum sickness or a clinically significant allergic drug reaction is suspected, Sponsor should be notified and serum for ATAs should be drawn and sent to the central laboratory. ATA samples may be used for assessment of etrolizumab serum concentration.
- ^f Administer before other assessments.
- ^g If clinically indicated.
- ^h Neurologic examination consists of the PML Subjective Checklist and the PML Objective Checklist, as per [Appendix 8](#).

Appendix 3 Extended Progressive Multifocal Leukoencephalopathy Safety Monitoring (SM, Part 2) Schedule of Assessments

Part 2 (SM)	92-week Extended PML Monitoring Period ^a
	24, 48, 68, and 92 Weeks after Patient Discontinuation from Study OR Early Termination ^b
PML Subjective Checklist (Telephone Only) ^c	X
Adverse Event Reporting to Roche Safety Risk Management ^d	X

OLE-SM=open-label extension–safety monitoring; PML=progressive multifocal leukoencephalopathy; SM=safety monitoring.

Note: The extended PML monitoring period is to be conducted for patients completing or discontinuing from Part 1 (OLE) of the OLE-SM study AND for patients entering OLE-SM Part 2 (SM) from Study GA29144 after completion of 12-week safety follow-up in Study GA29144.

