1. INTRODUCTION

The analyses described in this Statistical Analysis Plan (SAP) will supersede those specified in Protocol GA29145 for the purposes of reporting.

The purpose of this document is to describe the analyses for reporting out Part 1 of the Open-Label-Extension Safety Monitoring (OLE-SM) study for GA29145. This SAP will solely focus on reporting data collected during Part 1 (OLE) of GA29145.

This OLE-SM study is composed of two parts:

1. Part 1 is the OLE for eligible patients, during which etrolizumab, 105 mg SC, will be administered Q4W followed by a 12-week safety follow-up post-treatment.
2. Part 2 is the 92-week PML SM for all patients, during which no etrolizumab will be administered.

[figure not shown]
Patients who are enrolled in Part 1 (OLE) should participate in Part 2 (SM).

There may be patients from Study GA29144 who are ineligible for or choose not to participate in Part 1 (OLE) who will be asked to directly enroll in Part 2 (SM).

Key characteristics of the GA29145 OLE-SM are provided in [Table 1](#). Treatment arms and rollover of patients from induction/maintenance to GA29145 OLE-SM from parent CD studies are depicted in [Figure 1](#) and [Figure 2](#).

[figure not shown]
The maximum number of patients enrolled in GA29145 OLE-SM is approximately 1150 (i.e., all patients enrolled in Study GA29144). No formal sample size calculations were performed.

Figure 1 Study Schema for Part 1 (Open-Label Extension; OLE) of the OLE-SM Study

OLE=open-label extension; OLE-SM=open-label extension—safety monitoring; Q4W=every 4 weeks; Q12W=every 12 weeks; SC=subcutaneous.

Figure 2 Study Schema for Part 2 (Safety Monitoring; SM) of the OLE-SM Study

OLE=open-label extension; OLE-SM=open-label extension—safety monitoring; PML=progressive multifocal leukoencephalopathy; ~Q24W=approximately every 24 weeks.

Table 1 Key Characteristics of GA29145 OLE-SM in CD (Juniper)

Study	GA29145 (Phase III)	
Treatment (Number Exposed)	Open-label etrolizumab 105 mg SC Q4W (n= up to ~1150)	
Study Phases	OLE up to 10 years from FPI 12-week safety follow-up 92-week PML monitoring	
Key Eligibility Criteria	Part 1 (OLE)	Part 2 (SM)**

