4.2 SAFETY ANALYSES

Safety data will be assessed through descriptive summaries using the OLE population. All data available up until the clinical cut-off date (CCOD) will be reported.

Safety evaluations for the OLE population will include data from the first dose of treatment in Part 1 (OLE) until the patient completes/withdraws from the Part 1(OLE) of the study GA29145, this includes any 12-week safety follow-up data.

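### The SAP's concomitant-medication window closes 7 days after the last dose, short of the 28-day dosing interval, the protocol's own definition and the SAP's safety window

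*SAP*

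**What the plan says.** SAP 4.2.3.5 defines concomitant medications as those in use at any time "from first dose of OLE study drug through to 7 days after last dose of OLE study drug". It plans counts of patients and of medications, split by class and preferred name.

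Four other places bear on that end date:

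- SAP 1 gives the regimen: "105 mg SC, will be administered Q4W followed by a 12-week safety follow-up post-treatment".
- Protocol 4.3.1 describes concomitant therapy as any medication "used by a patient from the start of the study to completion/early withdrawal from treatment". Footnote f of Protocol Appendix 1 sets the timing of that visit: "To be performed within 30 days of last dose of study drug".
- SAP 4.2, the parent section of 4.2.3.5, runs safety evaluation from the first OLE dose until the patient completes or leaves Part 1, and "this includes any 12-week safety follow-up data". SAP 4.2.2 uses the same period for patient-years at risk.
- Protocol Appendices 1 and 2 collect concomitant medications at the completion or early withdrawal visit and again at Weeks 6 and 12 of safety follow-up.

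SAP 4.4, which lists changes to protocol-planned analyses, mentions only anti-therapeutic antibodies. The SAP gives no reason for the 7-day limit.

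**The concern.** A limit of 7 days closes the table while the patient is still inside an ordinary 4-week dosing interval. The days lost fall at the end of treatment, where changes of therapy are to be expected. Under Protocol 3.1.2, 4.3.2 and 4.5.2, a patient who takes a prohibited therapy must stop etrolizumab, so the preceding injection normally becomes the last dose. If the prohibited medicine began more than 7 days after that injection, the treatment that ended dosing is missing from the table meant to describe treatments.

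The interpretation of safety is also affected. Adverse events are counted through the 12-week follow-up, but therapies started after day 7 that might help to explain them are not summarised over the same period.

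**Working it through.** The plan states no figure for this point, so there is nothing to reproduce. The check is a comparison of windows, counted in days from the last OLE dose.

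**Inputs**

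- End of medication window: day 7 (SAP 4.2.3.5).
- Nominal dosing interval: 4 weeks = 28 days (SAP 1).
- Latest completion or early withdrawal visit: day 30 (Protocol Appendix 1, footnote f).
- Safety follow-up: 12 weeks = 84 days (SAP 1, Protocol Appendix 2).

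**Days not covered = comparison period − 7**

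- Last dosing interval: 28 − 7 = 21 days; 21/28 = 75%.
- To the latest withdrawal visit, the protocol 4.3.1 end point: 30 − 7 = 23 days; 23/30 = 77%.
- To the end of safety follow-up, the adverse event window, if the 12 weeks run from the last dose: 84 − 7 = 77 days; 77/84 = 92%. If they run from the withdrawal visit, as Protocol 4.4.3 can be read, the gap is up to 30 + 84 − 7 = 107 days.

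**Which medicines are lost**

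- Any medicine in use by day 7, including one that continues afterwards: counted.
- Permitted corticosteroid or immunosuppressant started between day 8 and day 28, next dose taken: counted, because the last dose, and with it the window, moves forward.
- The same permitted medicine, but the patient stops etrolizumab in that interval for some other reason: not counted.
- Prohibited therapy started between day 8 and day 28: not counted, because its use ends dosing and the window stays closed at day 7.

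The rule therefore omits prohibited therapy by construction and permitted rescue only when it coincides with stopping.

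**Exposure at the cut-off (context only)**

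Protocol 5.1.1.7 restricts live vaccines "for at least 5 half-lives (approximately 12 weeks) after final study drug administration". That implies a half-life of 84/5 = 16.8 days. Assuming simple first-order elimination, the fraction of drug remaining is 2^(−7/16.8) = 0.75 at day 7 and 2^(−28/16.8) = 0.31 at day 28. The 7-day limit is thus not explained by washout. These values enter no planned analysis.

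**The case against.** The strongest case against is that little depends on this table. The study has no hypothesis tests and reports in a synoptic CSR. No efficacy rule uses concomitant medication: evaluable patients who withdraw are already non-responders in the Hybrid LOCF and Non-Responder analyses, apart from those stopped by the sponsor's termination. Investigators judge causality patient by patient. The SAP also says that it supersedes the protocol's analyses, and Protocol Section 6 plans no concomitant-medication summary, so SAP 4.4 was arguably not bound to list the difference. All of this stands and limits the weight of the point. It does not explain why the window differs from the protocol's definition and from the SAP's own parent section.

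A second objection is that prohibited use can appear elsewhere. SAP 4.1.1 summarises reasons for discontinuation and major protocol deviations, and Protocol 4.5.2 requires the primary reason for stopping to be recorded. SAP 4.1.2 summarises corticosteroid and immunosuppressant use at baseline. It would therefore be wrong to call this table the only output on background or rescue treatment. Those outputs do not replace it, however. Permitted rescue is not a deviation, and baseline use says nothing about medicines started later.

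A third objection concerns the benchmark. Protocol 4.3.1 ends at completion or withdrawal from treatment, so the 92% figure measures misalignment with adverse event counting, not departure from the protocol's definition. This is right, and the 21-day and 23-day gaps are the ones to rely on.

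Finally, the sponsor terminated Part 1 on 15 February 2022, with last dosing on 15 May 2022. New therapy after closure may be replacement rather than rescue, so a longer window without separation would mix the two. This stands and shapes the fix.

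**Conclusion.** The inconsistency is real and worth correcting, with limited consequence. The SAP window leaves out medicines first taken after day 7: up to 21 of 28 days of the last dosing interval, or up to 23 of 30 days to the withdrawal visit. The effect is confined to one descriptive table and to reading adverse events against it. It is a gap in reporting, not in collection.

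Three stronger readings are tempting and not supported:

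- A reader might infer that three quarters of treatment-ending switches are missed. That only restates 21/28 under an assumed even spread of starts. The documents give neither the number nor the timing of switches, so the number of patients affected cannot be computed.
- A reader might infer that rescue with corticosteroids or immunosuppressants is generally lost. Protocol 3.1.2, 4.3.1 and 5.1.2 permit both, and their use does not force withdrawal.
- A reader might infer that remission rates are biased. No efficacy derivation uses this window.

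The conclusion assumes the nominal 28-day interval and a withdrawal visit as late as day 30. An earlier visit makes the gap to the protocol's definition smaller.

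**What to change.** In SAP 4.2.3.5:

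- Extend the on-treatment window from first OLE dose to the completion or early withdrawal from treatment visit, up to 30 days after the last dose, in line with Protocol 4.3.1.
- Put medicines first started after that visit, through the 12-week safety follow-up, in a separate column, so that the table can be read against the adverse event window in SAP 4.2.
- Show patients who stopped because the sponsor terminated the study separately. SAP 4.1.3 already identifies this group for the efficacy analysis.

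If the 7-day limit is intended, state the reason and record the difference from Protocol 4.3.1 in SAP 4.4.

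The cost is a changed date filter, one added column and one added split. No new data are needed. Reported medication use will be slightly higher.
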